In discussions (but not in the protocol), there was interest in exploring how COVID affected the outcome, in the sense that patients who became eligible when COVID was more prevalent (and elective care was less available) may have taken longer to have follow-up. Because this is a complicated topic and will distract from the main randomized results, it was decided to save such analyses for a subsequent manuscript. The current manuscript will simply adjust (through indicator variables) for 3-month time windows. Since COVID peaked in different areas at different times, these indicator variables will be included as interactions with study site (Boston versus Dartmouth).

Contents:

1. Exhibit 1: Figure 1: Consort Diagram
2. Exhibit 2: Table 1: Baseline Characteristics, by Arm
 - a. Patient characteristics
 - i. Sex
 - ii. Age
 - iii. Race/Ethnicity
 - iv. Primary insurance
 - v. Primary language
 - vi. Marital status
 - vii. Comorbidities
 - viii. Number of PCP visits in prior year
 - ix. Number of no show visits in prior year
 - x. Type of cancer
 - xi. Severity of screening abnormality
 - xii. Rurality (distance or population)
 - xiii.
 - b. PCP characteristics (from protocol; none currently in the prototype table):
 - i. Sex
 - ii. Provider type (MD/ DO, NP/ PA, other)
 - iii. Specialty
 - iv. Panel size (not risk adjusted)

- c. Clinic characteristics (from protocol; none currently in the prototype table):
 - i. Location (hospital; community health center)
 - ii. Visit volume at time of randomization
 - iii. Patient mix (% female; % Medicaid) at time of randomization

- 3. Exhibit 3: Table 2: Overall Primary (120 day completion) and secondary (240 day) outcome analyses
Intent-to-Treat and Modified Intent-to-Treat;
“Unadjusted” and Adjusted
 - a. Presentation: Data will be shown by arm, both ITT and mITT, both adjusted and “unadjusted”
 - i. The overall global p-value (<0.05) for the adjusted ITT analysis will be shown. If the global test is significant, then three pairwise tests (each arm against control/Arm 1) looking for $p<0.0167$.
 - ii. All other analyses and comparisons will be based on 95% confidence intervals

 - b. Primary and secondary analyses: SAS Proc GLIMMIX with the patient as the unit of analysis and a binary outcome (completed/not completed). All models (including “unadjusted”) will include random effects for practices and physicians. All models (including “unadjusted”) will include fixed effects for type of cancer. All models (including “unadjusted”) will include indicator variables for time (calendar month), along with interaction terms with site (Boston versus Dartmouth).
 - i. Unadjusted analysis: The model above will include random effects for practices and physicians, fixed effects for cancer types, fixed effects and interactions for calendar month and study stie, and indicator variables for Arms 2, 3, and 4.

 - ii. Adjusted analysis: The covariates from 2 above will be added individually to the model. Any that are significant at $p<0.05$ and change the coefficient of any of the 3 indicators for treatment arm by $>20\%$ will be retained in the model as confounders. (Type of cancer and calendar month will be retained in the model regardless of significance or confounding.) Adjusted completion rates will be calculated by marginal standardization and presented in the Table.

- 4. Exhibit 4: Figure 2: Forest plot with subgroup analyses for the primary (120 day completion) outcome

Intent-to-Treat
Adjusted only

- a. Presentation: Data will be shown by subgroup as an odds ratio (versus the control arm 1) with 95% confidence interval; ITT; adjusted only
 - i. P-values for interaction will be presented
 - ii. All other comparisons will be based on 95% confidence intervals
- b. Subgroup analyses: SAS Proc GLIMMIX with the patient as the unit of analysis and a binary outcome (completed/not completed). All models will include random effects for practices and physicians. All models will include fixed effects for type of cancer and calendar month.
 - i. Subgroups (each set analyzed separately):
Type of cancer (breast; cervical; CRC; lung)
Severity of abnormality (low; medium; high)
 - ii. Adjusted analysis: The model above will include random effects for practices and physicians, fixed effects for cancer types and calendar month, indicator variables for Arms 2, 3, and 4, indicator variables for the subgroups, and interaction terms for the arms-by-subgroups.
A global test for effect modification will be run and reported. However, regardless of significance, a separate “unadjusted” model will be run for each subgroup.
Since, some of the subgroup sample sizes will be limited, not all the covariates from the primary overall model above in (3) will be added to each stratified models. Decisions will be made based on the degree of confounding and the sample size.
- c. Appendix: A similar figure will be created for the mITT data. A decision of whether to display it in the appendix will be made based on the findings.

5. Exhibit 5: Figure 3: Kaplan-Meier Curves

- a. Four curves (4 arms), unadjusted, ITT
- b. Log-rank p-value
- c. A Cox regression model will be built for the ITT data. Since only one level of clustering is available, the model will use the analogue of random effects for practices and adjust for the same variables as in the logistic regression model above.
 - i. Significance testing will use a global p-value across all 4 arms and, if significant at $p<0.05$, pairwise comparisons between each arm and the control arm will be carried out. Results for the pairwise comparisons will be presented as 95% confidence intervals.
 - ii. The results of the Cox regression will be reported in the text. A table of the model results may appear in the Appendix.

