Inclusion criteria: Individuals who have an abnormal screen that is due for follow-up including:

- Breast: women 40-80 years with an *incident* (i.e., newly detected) abnormal screening mammogram or digital breast tomosynthesis (DBT) exam.
- Cervical: women 21-65 years with an *incident* abnormal screening Pap.

- Colorectal: adults 40-80 years with an abnormal screen, including *incident* FOBT/ FIT, or *prevalent* colonoscopy. Because of the long periods of time required for follow-up of colonoscopies, we will look back over a 5-year period and will therefore find *prevalent* abnormalities that become due for follow-up.
- Lung: adults 55-80 years, current and former smokers, with an *incident* abnormal LDCT result.

Definition of the specific screening abnormalities and timing of diagnostic evaluation are based on our prior work, expert opinion, and the literature. Need for follow-up will be determined by the lack of an appropriate clinical test within the specified time as documented in the EHR.

Exclusion criteria: We will exclude patients who: 1) are not English or Spanish-speaking, or 2) have had prior cancer of the organ for each screening test (i.e., women with prior breast cancer will not be tracked for breast cancer screening abnormalities) as these individuals may have non-standard follow-up care recommendations.

Intervention Design and Randomization Scheme. We will perform a 4-arm cluster RCT with randomization done at the practice-level, across the participating practices. We have chosen this level of randomization as it would be logistically complicated for the practices to have different patients randomized to different intervention components (i.e., reduced contamination). While we have received the approval of the primary care network leadership of the participating networks and have discussed the study with practice leadership, practices will be given the opportunity to opt-out of the study before practices are randomized. Randomization will be stratified based on: (1) practice size, (2) percent female, and (3) percent of patients on Medicaid as a marker for socioeconomic status.

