The primary analysis model will be a random effects logistic regression, implemented through the SAS Glimmix procedure. Timely follow-up (yes/no) will be the patient-level outcome and random effects for practice and physician will allow for exchangeable correlation between patients seen within the same practice and by the same physician. The primary fixed predictors will be 3 indicator variables representing the 3 intervention arms and we will use a global likelihood ratio test to compare the 4 study arms. If the global test is significant ($p < 0.05$), we will compare the intervention arms to the control group (our primary comparisons with a Bonferroni-adjusted significance level of 0.0167) and to each other (secondary comparisons). Comparisons to the control arm will capture the cumulative effects of the interventions, while comparisons between the intervention arms will capture the marginal effects of each level of intervention. We will include covariates for the type of cancer, level of initial screening abnormality, and any patient, provider or practice characteristics which are identified as confounders.

Results will be presented as adjusted follow-up rates, with 95% confidence intervals, calculated using marginal standardization.

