After our study, we found that the Health Maintenance Modifiers we created were placed on 259 patients' charts by their clinicians (outside of our research). There is no functionality built in Epic to remove these modifiers when an appropriate follow-up test was received by a patient unless they were part of our study. Our study has now ended, and we have removed the health maintenance modifiers that we created. Because we didn't create the modifiers for these 259 patients, we are concerned that they will linger even if a patient has received appropriate follow-up. We will contact anyone in the Epic HMM Audit User list and ask them to review the modifier and either replace it with other functionality available in Epic or remove it. We will send 2-3 reminders over the course of 4-6 weeks. The last reminder will inform them that the modifier will be removed by our study staff.

Describe explicitly the methods for ensuring the safety of subjects. Provide objective criteria for removing a subject from the study, for example, objective criteria for worsening disease/lack of improvement and/or unacceptable adverse events. The inclusion of objective drop criteria is especially important in studies designed with placebo control groups.

This protocol is minimal risk, as it is designed to improve the quality of care for patients with an abnormal cancer screening test result that is overdue for follow-up. Automated outreach (by Patient Gateway or letters) will provide information for patients to contact their PCP's office to arrange for needed follow-up. Patients in Arm 4 who are contacted by the study outreach administrator or navigator who say that they do not want further evaluation will not be contacted further by study staff. Participants selected for the surveys will be informed that they can refuse participation at any point.

FORESEEABLE RISKS AND DISCOMFORTS

Provide a brief description of any foreseeable risks and discomforts to subjects. Include those related to drugs/devices/procedures being studied and/or administered/Performed solely for research purposes. In addition, include psychosocial risks, and risks related to privacy and confidentiality. When applicable, describe risks to a developing fetus or nursing infant.

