Trial: We plan to recruit 3324 participants in the RCT who fit the eligibility criteria defined above (are overdue for follow-up of an abnormal cancer screening test result). Because the trial is testing a “care enhancement” we are requesting a waiver of informed consent given the large number of subjects distributed over a maximum of 44 primary care practices. Randomization will be done at the practice level and individual patients will not be approached for recruitment. Because randomization will be done at the practice level, we will not be able to recruit exactly 3324 individuals (patients may be in process of recruitment since they will be recruited in batches) – this is the number suggested by our sample size calculation. We will not exceed recruitment of 12,000 eligible individuals. The outcomes for the main trial will be assessed using data from the electronic health records at BWH, Faulkner, MGH, NWH, NSMC, and DFCI. NWH, NSHM, and DFCI are included because patients from MGH and BWH may have tests that are performed at these sites, thus they will be included in our review for diagnostic testing. Because of the large number of study participants and the minimal risk, we request a waiver of informed consent for this portion of the trial. It would not be feasible to contact this number of individuals and as this is a pragmatic trial it would adversely affect the validity and interpretation of our results.

Surveys: Some of the outcomes of the study will be measured by PCP and patient surveys:

PCP Surveys-PCPs, excluding trainees, at participating sites using the electronic health record will be surveyed prior to launch of the RCT and 3 months after recruitment ends. Prior to fielding the survey, we will request that the primary care network director send an email to PCPs in his/ her network informing them about the purpose to the survey-will then receive an email from one of the study investigators with a link to a Redcap survey. Each PCP will receive up to 5 email contacts over 4 weeks. Remuneration is described in the appropriate section below.

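### The protocol's global likelihood ratio test has no small-sample correction for at most 44 practices, so its level is about 6-7% unless the practice ICC is near zero; the SAP names no test, fitting method or df

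*Combined protocol and SAP*

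**What the plan says.** Randomisation is by practice to four arms (protocol, Intervention Design and Randomization Scheme). That section adds: "Randomization will be stratified based on: (1) practice size, (2) percent female, and (3) percent of patients on Medicaid". Under Recruitment Procedures, patients are "distributed over a maximum of 44 primary care practices".

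The protocol's Analysis Plan/ Sample Size fits a random effects logistic model in GLIMMIX, with practice and physician as random effects and three arm indicators. For the global comparison, "we will use a global likelihood ratio test to compare the 4 study arms". If p<0.05, each intervention arm is compared with control at 0.0167. No reference distribution, df or estimation method is stated.

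SAP Contents item 3 keeps the gate: "The overall global p-value (<0.05) for the adjusted ITT analysis will be shown", followed by pairwise tests at 0.0167. Its model is "SAS Proc GLIMMIX with the patient as the unit of analysis and a binary outcome". Every model also has cancer type, calendar month, site and month-by-site terms. The SAP does not repeat the likelihood ratio test and names no other test, fitting method or df for this outcome.

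Neither model includes the randomisation strata by design. SAP Contents item 2.c lists visit volume, percent female and percent Medicaid as clinic characteristics. Item 3.b.ii tries the listed covariates one at a time; those with p<0.05 that also move any arm coefficient by more than 20% "will be retained in the model as confounders". The protocol has its own rule, based on imbalance between arms and a 20% change in the effect estimate.

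**The concern.** Arms differ only between practices, so the information about arm effects is limited by the number of practices, not of patients. With 44 practices and four arms there are at most 40 between-practice df, and fewer if practices opt out. A likelihood ratio test is ordinarily referred to chi-square on 3 df. That treats the between-practice variance as known, and maximum likelihood also underestimates it. Both push the level above 5%.

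The SAP does not settle the matter. Likelihood ratio, Wald and F tests, on practice-level or much larger df, are all compatible with its text, and their levels differ. A likelihood ratio test also needs a true likelihood fit (Laplace or quadrature) rather than pseudo-likelihood, so the unnamed fitting method matters. At stake are a headline p-value and the gate to every primary comparison.

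**Working it through.** **Inputs from the documents.** At most 44 practices; four arms; global alpha 0.05; pairwise alpha 0.0167; 3,324 patients, about 831 per arm; 80% power for an 11-point difference; background follow-up of about 50%. The documents give no ICC, number of physicians per practice or coding of the strata, so these are assumed below.

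**The plan's own figure.** The 3,324 can be neither confirmed nor refuted without an ICC. It does imply one if 50% vs 61% is assumed. Without clustering, that contrast needs 320 per arm at alpha 0.05 or 426 at 0.0167. The design effects are 831/320 = 2.60 and 831/426 = 1.95. With 3,324/44 = 75.5 patients per practice and design effect 1 + 74.5 x ICC, the implied ICC is about 0.021 or 0.013.

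**Closed-form level** (equal practices, normal practice means, between-practice variance dominant). With m practices and q further practice-level terms, let d = m - 4 - q. Then LRT = m x ln(1 + 3F/d), with F distributed as F(3, d). The test rejects when LRT > 7.815, that is, when F > (exp(7.815/m) - 1) x d/3.
- m = 44, q = 0 (no site): F > 2.591 on (3, 40) df; level 6.6%. The correct 5% point is 2.839.
- m = 44, q = 1 (site): F > 2.527 on (3, 39) df; level 7.15%.
- m = 44, q = 4 (site and three one-df strata): F > 2.332 on (3, 36) df; level 9.0%.
- m = 36: 7.0% without site, 7.7% with site.

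A 0.0167 pairwise test using z where t on 40 df applies has level 2.15%.

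**Level by practice ICC** (simulated normal model, 44 practices x 6 physicians x 12 patients, physician share of variance 0-3%, variances bounded at zero, 40,000 runs per cell):

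| Practice ICC | LRT, no site | LRT, site |
|---|---|---|
| 0.001 | 4.4-4.8% | 4.8-5.0% |
| 0.005 | 5.8-6.0% | 6.1-6.4% |
| 0.01-0.05 | 6.3-6.9% | 6.8-7.3% |

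A logistic simulation with a practice effect only, 44 practices and 3,324 patients (4,000 runs) agrees: 3.8% (+/-0.6) at ICC 0; 6.1% (+/-0.7) at ICC 0.0127; 6.8% (+/-0.8) at that ICC with practice-size CV 0.7.

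**Strata** (three binary strata, blocks of four, 44 practices, site in the model). If the strata are never fitted and explain 0/10/20/30% of practice-mean variance, the likelihood ratio test runs at 7.0/5.5/3.9/2.6%. That is not the SAP's rule. Under the null the arm coefficients are near zero, so a 20% change is easily reached, and prognostic strata tend to pass p<0.05. With the retention rule applied, at least one stratum is kept in 48/71/85% of runs at shares of 10/20/30%. The level stays at about 5.7-7.8% over shares of 0-30%.

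**Any false primary claim, global null.**
- Likelihood ratio test plus z, with site and the retention rule: 4.6/3.9/3.5/2.9% at shares of 0/10/20/30%.
- The same tests with site and all strata fitted: 5.9-6.2%.
- F plus t with site and all strata: 2.9-3.2%.

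**Level of the F test.** With site and strata fitted it runs at 4.7-5.1% for shares of 0-30%. With the practice variance bounded at zero it is conservative at low ICC: 2.7-3.1% at 0, 3.2-3.4% at 0.001 and 4.4-4.5% at 0.005.

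**The case against.** The strongest reply is that the global p-value is only a gate. A primary claim also needs p<0.0167 against control, and by the figures above the chance of any false claim is already 5% or less. The fix takes it to about 3%, further from 5%. This stands, and it is why the point is minor. It does not rescue the global p-value, which the SAP will report against 0.05.

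A reader might infer that leaving the strata out pushes the SAP's test well below 5%, so that the two errors cancel. The documents do not support this: the SAP's own covariate list and retention rule can bring those characteristics in, and the simulated level then stays above 5%.

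A reader might also infer that the SAP changed the protocol's test. It is silent, and it refers back to the protocol several times, so the likelihood ratio test may still be intended. Likewise, no document says that the pairwise tests use z; that is an assumption here.

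Finally, a new primary test chosen after the study ended is itself a late choice. That is a fair objection, and disclosure with both tests reported is the answer to it. Nor does the F test fix the level at exactly 5%: it is conservative when practices hardly differ.

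**Conclusion.** The point holds and is minor. Referred to chi-square on 3 df without correction, the protocol's global test runs at about 6-7% at appreciable practice ICC, including the 0.013-0.021 implied by the sample size under 50% vs 61%. It runs at about 4-5% only near zero ICC. With the SAP's site term and retention rule, about 6-8% is expected whether the strata explain 0 or 30% of practice variance. The SAP leaves the test, fitting method and df open.

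The reported global p-value is therefore slightly too small. The documents do not support a claim that false primary findings become materially more likely: under the global null that risk stays at about 5% or less.

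The closed forms rest on equal practices and dominant between-practice variance. The other levels rest on assumed ICC, physician numbers and strata coding. The strata simulations use normal practice means, and selection among the SAP's other covariates was not simulated.

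**What to change.** In the protocol's analysis plan and SAP Contents item 3:
- Replace the likelihood ratio test with an F test of the three arm indicators on practice-level df. Between-within df are practices - 4 - practice-level terms: 44 - 4 - 1 - 3 = 36 with site and three one-df strata. Kenward-Roger df are an alternative. Use matching t tests at 0.0167 and t-based intervals.
- Include practice size, percent female and percent Medicaid, coded as at randomisation, as fixed effects with site by design.
- Make both changes together. Adding the strata while keeping the likelihood ratio test raises its level to about 9%.
- State the fitting method and df, and note that the F test is conservative (about 3%) if the practice ICC is near zero.

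The protocol records "Our study has now ended". Date and disclose the change, state whether outcomes by arm had been seen, and report the protocol's likelihood ratio test alongside.

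**Cost.** No new data, though the fitting method may change. Intervals are about 3% wider than z intervals with the same variance estimate, and 10-14% wider than z intervals using the maximum likelihood variance. Simulated two-step power for arm 4 vs arm 1 assumed 50% vs 61%, ICC 0.013, and arms 2 and 3 at one third and two thirds of the effect. The likelihood ratio test plus z with site gives 77-79%, partly because it runs above its level. F plus t with site and strata gives 68%, 76% and 82% if the strata explain 0, 10 and 20% of practice variance. Power is therefore lost mainly if the strata are not prognostic.

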The 4-arm design will allow us to compare “standard care” (Arm 1) to three intervention arms that represent the sequential/ stepped addition of: (Arm 2) a system-level, visit-based intervention consisting of PCP facing reminders deployed when a patient is overdue for follow-up (health maintenance reminders; automated problem list additions); (Arm 3) the addition of a population-based intervention with study staff administration of the patient and PCP facing reminders deployed when a patient is overdue for follow-up regardless of whether they come in for a visit (e.g. bulk In-Basket messaging to the PCP, Patient Gateway reminders or letters, a brief phone call or voice message for the patient); and (Arm 4) the addition of a team-level intervention including phone calls from an outreach coordinator and a patient navigator. Part of the role of the Patient Navigator will be to assess a patient’s social determinants of health. If the patient has any needs the patient navigator will use “Aunt Bertha” an online platform to help patients find social services in their area. Patients in Arm 1 will receive the usual care provided by their PCP. Given our stepped care approach, this randomization

scheme will allow us to compare the cumulative addition of each level of intervention to standard care as well as the marginal effect of each additional level to the prior group. This design allows us to evaluate changing the responsibility for “opportunistic” follow-up, typically by the PCP at the time of a visit (Arm 1), to a systematic, multilevel approach, examining the cumulative and marginal effects of each subsequent level of intervention. In addition to the multilevel components, the individual- and team-level engagement algorithm will take a “stepped care” approach with increasing level of intensity of engagement.

Recruitment and Enrollment. Key organizational components of the study will involve:

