(1) Practice and Provider Engagement. We have obtained support of network leadership for the study. Investigators have/ will attend practice meetings at intervention sites to integrate work flow with practice routines and educate staff about the study and its procedures. PCPs will not be required to do recruitment; identification of eligible patients will be done centrally using the IT platform described above. We therefore anticipate a high level of practice and PCP participation since the intervention does not constrain usual practice, but adds additional systems beyond those currently available. As noted above, practices and providers will be given the opportunity to opt-out of the study before practices are randomized.

(2) Patient Identification and Enrollment. The mFOCUS platform will incorporate algorithms to identify eligible patients and patient-practice attribution. All patients will remain under the direction of their personal PCP/ practice and the intervention components will facilitate the delivery of care in addition to the current standard of care.

We plan to enroll 3324 eligible participants (approximately 831/ arm – as randomization will be done at the practice level the arms will not be the same size) across the 3 participating primary care networks (BWH, MGH, and Dartmouth). We anticipate that recruitment will be somewhat higher at BWH and MGH than Dartmouth as the networks are bigger. Because randomization will be done at the practice level, we will not be able to recruit exactly 3324 individuals (patients will be in process of recruitment since they will be recruited in batches) – this is the number suggested by our sample size calculation. We anticipate that this calculations will need to be updated due to the impact of COVID-19 and that our recruitment number will be higher because of the back log of testing that will occur as hospitals reopen for screening procedures. We anticipate that we could possibly enroll up to 9,000 eligible patients at MGH/BWH, and 12,000 eligible patients study wide. We will not exceed recruitment of 12,000 eligible individuals. Due to the way our IT system is configured, we anticipate that we could review up to 20,000 patient charts study wide. Not all of the patient charts reviewed will be deemed eligible.

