Our sample size calculation was based on an increase in the follow-up test completion rate of 11-14% with the intervention- this would give us 80% power to detect an 11% difference in the follow-up rate. We have an adequate number of potential participants across our sites to achieve this sample size.

Specific Aim 2: To evaluate facilitators and barriers to the *Reach, Adoption, Implementation and Maintenance* of mFOCUS.

The RE-AIM framework (Reach, Effectiveness, Adoption, Implementation and Maintenance with Effectiveness assessed in **Aim 2**) will allow us to assess the multilevel implementation of our intervention. The primary goal is to inform and facilitate dissemination of the program in the 3 networks rather than to test specific hypotheses. We will calculate summary statistics and conduct bivariate comparisons across sites using Fisher's exact test, t-tests, and the Wilcoxon rank sum test where applicable for survey outcomes.

RE-AIM Metric	Measure	Data Source
Reach	• % of eligible individuals in each intervention group who engage in relevant step (open email reminder, speak with outreach coordinator or PN)	• Population management system
	• Patient barriers and facilitators of follow-up	• Patient survey
Adoption	• Barriers and facilitators to follow-up • Systems & processes for follow-up • Knowledge of and satisfaction with components of mFOCUS	• PCP survey
Implementation	• Technical and organizational barriers to implementation • Fidelity of delivery of the intervention	• PCP survey • Population management system
Maintenance	• Technical and organizational barriers to maintenance	• PCP surveys

Patient, and provider surveys are attached. Once the final version of the patient survey is approved it will be translated by an IRB approved vendor and submitted to the IRB.

Briefly describe study procedures. Include any local site restrictions, for example, "Subjects enrolled at Partners will not participate in the pharmacokinetic portion of the study." Describe study endpoints.

See study procedures described above. No local site restrictions are planned.

For studies involving treatment or diagnosis, provide information about standard of care at Partners (e.g., BWH, MGH) and indicate how the study procedures differ from standard care. Provide information on available alternative treatments, procedures, or methods of diagnosis.

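### The three comparisons with control use a flat 0.0167; Holm keeps the same 5% family-wise limit and shows the second and third effective arm more often

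*Combined protocol and SAP*

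**What the plan says.** The protocol (Analysis Plan/ Sample Size) runs a global likelihood ratio test of the four arms at 0.05. If that is significant, each intervention arm is compared with control: "our primary comparisons with a Bonferroni-adjusted significance level of 0.0167". Comparisons between intervention arms are secondary.

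The SAP (Contents, item 3.a.i) gives the same rule, "If the global test is significant, then three pairwise tests (each arm against control/Arm 1"), each at p<0.0167. Item 3.a.ii adds: "All other analyses and comparisons will be based on 95% confidence intervals". Neither document mentions a stepwise procedure.

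On power, the protocol assumes an increase of 11 to 14 points and states that "this would give us 80% power to detect an 11% difference in the follow-up rate". It does not say at which significance level. The section on intervention design says the trial will "compare the cumulative addition of each level of intervention to standard care".

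**The concern.** The three contrasts with Arm 1 are the primary comparisons, and the arms are cumulative steps. How many of them beat usual care is therefore a main question: a reader will want to know whether the lighter steps work, as well as the full package.

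A flat 0.0167 charges every comparison the full price of three tests, even after one or two null hypotheses have been rejected. Holm removes that charge as it proceeds. At stake is the power to show the second and third effective arm. The chance of any finding at all and the comparisons between adjacent intervention arms are not affected.

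**Working it through.** **Inputs from the documents.** Three comparisons with one shared control; global gate at 0.05; 80% power for 11 points; effects of 11 to 14 points; about 831 patients per arm, hence roughly equal allocation; at most 44 practices.

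**Assumptions.** Two-sided tests, equal precision in the arms (so the three contrasts have correlation 0.5), and normal statistics unless stated. The alpha behind the 80% power is not given, so both readings are used.

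**The plan's own figure.** 0.05/3 = 0.0167, as stated.

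**Holm never shows fewer arms.** Its thresholds on the ordered p-values are 0.05/3 = 0.0167, 0.05/2 = 0.025 and 0.05/1 = 0.05. None is below 0.0167, so each Bonferroni rejection is also a Holm rejection. Keeping the global gate can only remove rejections, so the 5% control survives.

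**Standard error of a contrast.** SE = 0.11/(z for alpha + z for power).
- A, power set at 0.0167: 0.11/(2.394 + 0.842) = 0.0340.
- B, power set at 0.05: 0.11/(1.960 + 0.842) = 0.0393.

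**Chance of showing all three arms** (1,000,000 simulated trials per scenario, gate kept, present rule to Holm):

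| Setting | 11/11/11 points | 11/12.5/14 points |
|---|---|---|
| A | 61% to 77% | 74% to 86% |
| B | 42% to 59% | 55% to 72% |
| A, SE 20% smaller (assumed larger sample) | 88% to 95% | 94% to 98% |
| A, t tests on 40 df (44 practices less 4 arms) | 57% to 74% | 70% to 84% |

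The third row is there because the protocol expects more patients than 3324: "We anticipate that this calculations will need to be updated due to the impact of COVID-19". The fourth reflects patients "distributed over a maximum of 44 primary care practices".

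**Other measures, under A with the gate kept.**
- At least one arm at 11/11/11: 92.9% under both rules.
- At least two arms at 11/11/11: 83.9% to 87.5%.
- Two effective arms (11 and 14 points), both shown: 78% to 83%.
- One effective arm (11 points): 79.4% to 79.5%.
- Weak first step (5, 11 and 14 points; the 5 is assumed): at least two arms 79% to 83%, all three 17% to 30%.

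**Family-wise error, present rule to Holm.**
- No arm effective, gate kept: 2.9% under both.
- One overwhelmingly effective arm, two null: 3.1% to about 4.6%.
- Two overwhelmingly effective arms, one null: 1.7% to 5.0%.

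**The case against.** - **It is a preference.** The plan's rule is standard, prespecified and conservative, and nowhere is success defined as all three arms beating control. That measure shows Holm at its best; the mean number of arms shown at 11/11/11 under A moves only from 2.38 to 2.57. This is fair on size, and the smaller gains are listed above. It does not alter the fact that Holm can only add rejections, at no cost in patients.

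- **The flat rule leaves a reserve.** There are few practices and no stated small-sample degrees of freedom, so the p-values may be too small. If normal cut-offs are used where t on 40 df is right, a 0.05 test has size 5.7% and a 0.0167 test 2.1%. With two very effective arms and one null, Holm would then exceed 5% and the flat rule would not. The arithmetic is right, but the remedy for miscalibrated p-values is to calibrate them. The 40-df row shows that the gain remains when that is done.

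- **Holm is not the most powerful choice.** With the global gate kept, closed testing would allow 0.025, 0.025 and 0.05; with one effective arm at 11 points this raises power from 79% to 83%. That is correct, and it shows that still more could be gained. It is no argument for the flat rule.

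- **Intervals.** The 95% intervals in the plan are for adjusted arm rates and for the other comparisons; none is explicitly planned for the three primary contrasts. This stands, and the fix is worded accordingly. Nor do the documents plan the simultaneous intervals that would be the usual reason to prefer Bonferroni.

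- **Timing.** The protocol says "Our study has now ended". This is the most serious limit: nothing in the documents shows whether arm-level results are still unseen.

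**Conclusion.** The point holds as an efficiency improvement that should be made if timing allows. The present rule is valid. Holm dominates it under the same assumptions.

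With all three arms effective at the planned sizes, the chance of showing all three rises by about 12 to 17 points, whichever alpha the power calculation used. The gain is about 4 to 7 points with the assumed larger sample, about 4 to 6 points for showing both of two effective arms under A, and almost nothing with a single effective arm.

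That Holm never shows fewer arms and keeps the 5% limit requires only valid individual p-values. The sizes rest on the assumed alpha, equal precision, two-sided tests and the effect patterns shown.

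**What to change.** In the protocol's Analysis Plan and SAP item 3.a.i, replace the flat 0.0167 with Holm at family-wise 0.05 for the three comparisons with Arm 1: the smallest p-value against 0.0167; if significant, the next against 0.025; if significant, the last against 0.05. Report Holm-adjusted p-values. State that any 95% intervals shown beside them are not adjusted for multiplicity and may disagree with the Holm decisions.

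Dropping the global gate is a separate, optional change. It is not needed for error control. With all three arms effective at the planned sizes, dropping it adds 0.7 to 2.1 points (A) or 2.1 to 4.4 points (B) to the chance of at least one significant arm.

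Make the change by dated amendment, with a statement that arm-level results have not been seen. If they have, keep 0.0167 as the primary rule and label the Holm-adjusted p-values supplementary.

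The cost is one sentence in each document and no extra data or patients. When some arms are effective and others are not, family-wise error rises from 1.7–3.1% towards, but not beyond, the 5% that the plan already allows.
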